4.5. STUDY SCHEDULE

TIMETABLE OF THE STUDY

Actions	J0 Inclusion visit	Between D0 and M6	M6	Between M6 and M12	M12
Patient information	X				
Collection of written consent	X				
Background	X				
Randomisation	X				
Clinical examination and questionnaires ¹	X		X		X
Encouragement to continue physical activity			X		
Physical activity with activity trackers		X	X	X ²	X ²
Analgesic treatments	X		X		X
Adverse events		X	X	X	X

¹EVA, DN4, HAD, WPI, SSS, impedance measurement, Tampa, FIQR, EQ-5D-5L

² Depending on the patient's choice

4.6. *IDENTIFICATION OF ALL SOURCE DATA NOT IN THE MEDICAL RECORD*

- Physical activity: practice at inclusion and type of activity
- Questionnaires: FIQR, DN4, Tampa, HAD, WPI, SSS, EQ-5D-5L
- EVA
- Physical activity during the study according to the randomisation arm (% success)
- Impedance measurement

4.7. *RULES FOR STOPPING A PERSON'S PARTICIPATION*

Criteria for premature termination of a person's participation in research

Any patient included in the protocol who no longer wishes to participate will be prematurely withdrawn from the study as soon as the request is made.

For the modalities and duration of the follow-up of the early leavers, see the statistical section.

- Withdrawal of patient consent at any time during the study, before publication of results.
Right to object to the use of the data at any time during the study, before publication of the results

Procedures for premature termination of a person's participation in research

For details of how to use the data of people who stopped the study prematurely, see the statistics section.

Criteria for stopping part or all of the research (excluding biostatistical considerations)

Part or all of the study may be stopped permanently or temporarily by decision of the ANSM, the CPP or the study sponsor.

A written confirmation will be sent to the coordinating investigator of the study (specifying the reasons for premature termination) and to the principal investigator of each centre if applicable.

5. DATA MANAGEMENT AND STATISTICS

5.1. COLLECTION AND PROCESSING OF STUDY DATA

Data collection

One observation book (eCRF) will be created per patient. All information required by the protocol should be provided in the eCRF. It should include the data needed to confirm compliance with the protocol and all data needed for statistical analysis; it should identify major deviations from the protocol.

The persons responsible for filling in the eCRFs (investigator, CRA, etc.) must be defined and are identified in the table of delegation of responsibilities for each centre (kept in the investigator's folder).

Data coding

By signing this protocol, the principal investigator and all co-investigators agree to keep confidential the identities of the patients who participated in the study.

The transmission of a person's data for research purposes will therefore only be possible if a coding system is applied; the presentation of the research results must exclude any direct or indirect identification.

The identification of patients will be done according to the order of inclusion of patients by a number automatically assigned by the Clinsight software (eCRF) and then completed by the patients' initials.

This code will be the only information that will appear on the eCRF and will allow the eCRF to be linked to the patient afterwards.

The Research Manager is also required to code patient data on any documents he/she may have in his/her possession that are attached to the CRF.

A mapping table will be set up in each centre. This table will be kept in a secure location by the centre's principal investigator and will contain the patient code and patient data in order to be able to trace back to the patient file in case of missing or erroneous data. No clinical data will be collected in these correspondence tables.

Data processing

The collection of clinical data will be based on the setting up of a database and the creation of data entry masks similar to the observation book in accordance with the protocol and regulations currently in force.

The structure of the database and input screens will be approved by the Research Manager.

5.2. *STATISTICS*

Description of the planned statistical methods, including the timing of planned interim analyses

All variables will be described globally and by group. The description will include the numbers and percentages of modalities for qualitative variables and the minimum, maximum, mean, standard deviation and median for quantitative variables.

Main criterion

The patients' quality of life will be measured using the FIQR questionnaire at D0, M6 and M12. The evolution of the score at 6 and 12 months will be characterised by a graph and compared between the 2 groups using a linear regression model taking into account the baseline score at D0, the time effect, the "time*group" interaction and the repeated nature of the data.

The comparison of the evolution of the score at M6 will be tested from the M6 contrast.

Secondary criteria

The evolution of pain will be graphically characterised and compared using a mixed linear regression model taking into account the baseline data of the D0 score and the repeated nature of the data.

Neuropathic pain will be assessed using the DN4 questionnaire score. It will be compared between the two groups using a mixed generalized linear regression model taking into account the repeated nature of the data.

The evolution of the isochrony will be characterised graphically and compared using a mixed linear regression model taking into account the baseline data J0 and the repeated nature of the data.

The evolution of anxiety will be assessed from the total HAD score and compared between the two groups using a mixed linear regression model taking into account the baseline D0 score and the repeated nature of the data.

The evolution of pain on muscle compression will be assessed from the total WPI score and compared between the two groups using a mixed linear regression model taking into account the baseline score on D0 and the repeated nature of the data.

The severity of symptoms will be measured from the SSS score and compared using a mixed linear regression model taking into account the baseline data of the D0 score and the repeated nature of the data.

Physical activity monitoring will be collected every month until M12. Each month, the percentage of goal achievement will be calculated. The average percentage of success will be plotted and compared between the 2 groups using a mixed linear regression model taking into account the repeated nature of the data.

The evolution of lean body mass will be collected at D0 M6 and M12 and compared using a mixed linear regression model taking into account the repeated nature of the data.

The evolution of kinesiophobia will be assessed using the TAMPA self questionnaire at D0, M6 and M12. The total score will be compared between the groups using a mixed linear regression model taking into account the baseline score on D0 and the repeated nature of the data.

The evolution of the quality of life will be measured using the EQ5D-5L questionnaire at D0, M6 and M12. The evolution of the score will be characterised by a graph and compared between the 2 groups using a mixed linear regression model taking into account the baseline score on D0 and the repeated nature of the data.

Exploratory criterion

The evolution of the FIQR score will be evaluated using a linear mixed model taking into account the group and repeated nature of the data as well as the isochrony data at D0 in order to evaluate its predictive character.

Statistical justification of the number of inclusions

The study is a superiority trial on the decrease of the FIQR score (improvement of the quality of life) at 6 months between a control group (classic non-specific management in a common "multipathology" group) and an experimental group (specific management in a "fibromyalgia patients" group).

According to Hackshaw et al. (2016), the mean baseline QoL of the ten patients included was 49.4 (13.8) on the FIQR scale. After 6 months of intervention (life coaching including physical activity), the mean level of quality of life was 31.0 (13.2), i.e. a decrease in score of 18.4 points (37% decrease).

Evidence of a 7-point difference between the two intervention groups at M6 will be considered clinically significant.

With a power of 80%, and an alpha risk of 5%, 114 patients will be needed to show this difference. To ensure the necessary power, an additional 10% of patients will be included, for a total of 126 patients.

Expected level of statistical significance

The alpha risk is set at 5%.

Statistical criteria for stopping the research

NA

Method of accounting for missing, unused or invalid data

All missing data and the reason for it will be described in each group.

The FIQR score will be estimated and compared between the 2 groups using a linear model taking into account the repeated nature of the data, so no imputation method will be applied.

Managing changes to the original strategy analysis plan

NA

Selection of persons to be included in the analyses

The main analysis will be performed on the Intent-to-Treat (ITT) population, i.e. on all randomised patients. A sensitivity analysis will be performed on the Per Protocol (PP) population including randomised patients for whom no major protocol deviations were identified.

A data review meeting will be held to review and define the major criterion or not for each of the deviations.

Randomisation

Randomisation will be carried out in a 1:1 ratio and will be done in blocks.

Randomisation will be carried out in Ennov Clinical by connecting to the website: <https://www.dirc-hugo-online.org/csonline/>. The connection will be made through a login, a password and a study number, delivered by the data manager of the Research Unit of the La Roche sur Yon Hospital. The following information must be filled in:

- First initial of the name,
- First initial of the first name,
- Month and Year of birth,
- Compliance with inclusion and non-inclusion criteria (yes/no),

Randomisation will be carried out by the investigator after confirmation of the possibility of inclusion in the study. The inclusion number will be assigned automatically during randomisation.

An email confirmation will be sent to the person who performed the randomisation and to all persons involved.

The randomisation list will be carried out by the statistician of the Research Unit of the CHD of La Roche sur Yon. An explanatory guide to randomisation will be available online in Ennov Clinical

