2.2. OBJECTIVES AND SECONDARY EVALUATION CRITERIA

Secondary objectives

Compare between the 2 randomisation arms:

1. The evolution of pain intensity between the beginning of the treatment (D0), at 6 months (M6) and at 12 months (M12),
2. The presence of neuropathic pain and its evolution,
3. The evolution of isochrony between a physically executed and mentally simulated movement (Moseley, 2004; Moseley et al., 2008)
4. The evolution of anxiety and the presence of signs of the depressive series
5. The evolution of pain on muscle compression

6. The severity of the symptoms
7. Monitoring physical activity with activity trackers
8. The evolution of lean body mass measured on an impedance scale
9. The evolution of kinesiophobia
10. Changes in quality of life between the start of treatment (D0) and 12 months (M12)
11. Continuity of physical activity after the end of coaching

Secondary evaluation criteria

1. EVA at D0, M6 and M12
2. DN4 questionnaire score ≥ 4 at D0, M6 and M12
3. Difference between the duration of the performed movement and the imagined movement of picking up a magazine from a table at D0, M6 and M12
4. Hospital Anxiety and Depression scale (HAD) at D0, M6 and M12
5. Widespread Pain Index (WPI) (Häuser et al., 2017; Wolfe et al., 1990) at D0, M6 and M12
6. Symptom Severity Scale (SSS) (Häuser et al., 2017; Wolfe et al., 1990) at D0, M6 and M12
7. Percentage of success in achieving goals each month (M1-M12) as measured by activity tracker
 - (Duration in minutes per month at least 70% of the theoretical maximum heart rate $\times 100 / 240$ minutes
 - (4 weeks \times 60 minutes recommended = 240 minutes)
8. Percentage and weight of lean mass measured on an impedance scale at D0, M6 and M12
9. Tampa self-questionnaire (Knapik, Saulicz, & Gnat, 2011) at D0, M6 and M12
10. FIQR at D0 and M12 and EQ5D-5L at D0, M6 and M12
11. Level of physical activity between the groups between M6 and M12
 - (the duration in minutes per month between 50 and 60, between 60 and 70, between 70 and 80, between 80 and 90, and between 90 and 100% of the theoretical maximum heart rate measured with the activity tracker)

Exploratory secondary objective

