The isochrony between executed and imagined movement is a test inspired by the work of Moseley (2004) showing an alteration in the temporality of imagined movement in chronic pain patients. Patient positioning: initially, the patient has the upper limb and hand at the side of the body, with the feet 30cm from a table. A magazine is positioned by the operator flat, at the edge and not protruding from the table. First, the operator will ask the patient, "On my 'go' signal, you will take the magazine lying flat in front of you with your dominant hand and bring the limb back along your body at your comfort speed. When you have brought your limb back, you will say "stop". I will stop the clock at your end stop. This movement is to be done twice. The operator will note the 2 times in seconds and hundredths. In a second step, the operator will ask the patient: "At my starting "top", you will, without actually doing it and without moving, imagine taking with your dominant hand the magazine lying flat in front of you

and imagine bringing the limb back along your body at your comfort speed. When you have imagined bringing your limb back, you will say "stop". I will stop the clock at your end stop. This movement is to be done twice. The operator will note the 2 times in seconds and hundredths.

The Hospital Anxiety and Depression scale (HAD, Appendix 8) is a screening instrument for anxiety and depressive disorders. It consists of 14 items rated from 0 to 3. Seven questions relate to anxiety (total A) and seven others to the depressive dimension (total D), thus making it possible to obtain two scores (maximum score for each score = 21) (Zigmond & Snaith, 1983).

The Widespread Pain Index (WPI, Appendix 9) is a score given by the patient according to the number of affected areas (Häuser et al., 2017)

The Symptom Severity Scale (SSS, Appendix 10) is scored by the patient and includes headache, pain, cramp in the abdomen and depression (Häuser et al., 2017)

The percentage of target attainment will be calculated by averaging the attainment of monthly results, compared to clinical practice guidelines from the results recorded by the use of activity trackers

⇒ Duration in minutes per month at least 70% of the theoretical maximum heart rate x100 / 240 minutes
(4 weeks x 60 minutes recommended = 240 minutes)

The percentage (%) and dry mass (in kg) of lean mass will be measured on an impedance scale

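### Section 5.2 assesses anxiety on a total HAD score that section 4.3 does not define, and no separate between-group model is given for depressive signs

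*Combined protocol and SAP*

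**What the plan says.** Section 2.2 lists its secondary objectives under the lead-in "Compare between the 2 randomisation arms". Objective 4 reads "The evolution of anxiety and the presence of signs of the depressive series". The matching criterion is "Hospital Anxiety and Depression scale (HAD) at D0, M6 and M12", with no subscale named.

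Section 4.3 describes the HAD as 14 items, each rated 0 to 3, and sets out the scoring: "Seven questions relate to anxiety (total A) and seven others to the depressive dimension (total D"). Each dimension therefore has its own score, and the section puts the ceiling of each at 21. It describes no combined score.

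Section 5.2, under the secondary criteria, contains one HAD analysis: "The evolution of anxiety will be assessed from the total HAD score and compared between the two groups". The method is a mixed linear regression that allows for the D0 score and the repeated measurements. The same section opens with a general rule that every variable is described overall and by group.

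**The concern.** Objective 4 names two constructs and places both under a between-arm comparison. Section 4.3 supplies one score for each. Section 5.2 then plans a single model, calls its subject anxiety, and bases it on a score that 4.3 does not define.

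Two things are at stake. First, the anxiety result may not be attributable to anxiety, because half the items in a 14-item total are depression items. Secondly, a comparison that the protocol commits to has no analysis of its own. Because the wording can be taken in more than one way, the choice of score could also be made after the data are seen.

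**Working it through.** **Inputs.** From 4.3: 14 items, each scored 0 to 3, with 7 in total A and 7 in total D, and a stated maximum of 21 per score. From 2.2: objective 4 and criterion 4. From 5.2: the single HAD model.

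**Reproducing the plan's figure.** Maximum per score = items × maximum per item = 7 × 3 = 21, which agrees with 4.3. A sum over all items would have a maximum of 14 × 3 = 42. The supplied text gives no such score or range.

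**What a sum can show.** Change in sum = change in A + change in D.

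| Change in A | Change in D | Change in sum |
|---|---|---|
| −3 | 0 | −3 |
| 0 | −3 | −3 |
| −3 | +3 | 0 |

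The first two rows cannot be told apart on the sum, although only the first is a change in anxiety. In the third, a change in anxiety disappears. These values are arithmetic examples, not expected effects.

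**Which score is meant.** The text supports three readings.

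1. *The 14-item sum, reported as anxiety.* For the Tampa scale, 5.2 says "The total score will be compared between the groups using a mixed linear regression model", meaning the whole instrument, and it uses the total WPI score in the same way. On this reading 7 of the 14 items in the anxiety outcome measure depression.
2. *Total A.* Section 4.3 attaches the word total to each subscale. The anxiety model is then sound, but 5.2 does not say that this is the score, and nothing models total D.
3. *A joint measure for the whole of objective 4.* One objective, one criterion and one model could mean that the sum serves both constructs, with anxiety as shorthand. Depression items are then compared between arms, but only mixed with anxiety items, and neither construct has its own result.

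**Is depression modelled elsewhere?** The remaining secondary analyses in 5.2 contain no between-group model for total D or for the presence of depressive signs. According to 4.3, the SSS includes depression and the EQ-5D-5L has an anxiety/depression dimension, but each is analysed for a different objective. The opening rule of 5.2 gives summary statistics by group, not a comparison.

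**The case against.** The strongest defence is the joint reading: objective 4 has one criterion and one model, so depression is compared as part of the total. The by-group description adds to this. If total A and total D both count as variables, their means, standard deviations and medians would be shown by arm, and a reader could see which score had moved. Both arguments have force. They rule out saying that depressive signs go unexamined on every reading. They do not supply a separate comparison, and description by group is less than the comparison that 2.2 promises.

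A reader might infer three stronger claims, which the documents do not support:

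- *The anxiety analysis is certainly contaminated by depression items.* The sum is the more natural reading of 5.2, but total A remains possible, and on that reading the anxiety analysis is sound.
- *Using the sum costs power.* The documents give no HAD effects, standard deviations or correlation between A and D, so no power figure can be derived for this trial. If both scores move together, the sum may have more power than A alone. The problem is attribution.
- *The plan has no rule for the presence of depressive signs.* None appears in the supplied sections, but 4.3 places the HAD form in Appendix 8, which was not available. The absence of a cut-off is therefore not counted as a defect. A cut-off there would still not provide the missing model.

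**Conclusion.** The point holds. The score behind the anxiety analysis is not identified, and on all three readings depressive signs have no separate between-group model. This follows from comparing 2.2, 4.3 and 5.2, and needs no assumption about HAD data.

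Its size is limited. It affects the interpretation of one of eleven secondary criteria. The FIQR primary analysis, the sample size and the data collection are untouched. The sponsor should correct it because a stated objective lacks its analysis and the correction is simple.

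**What to change.** In 5.2, replace the HAD sentence with text to this effect:

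> Anxiety (HAD-A, total A, 0–21) and depressive signs (HAD-D, total D, 0–21) will each be compared between the two groups with the stated mixed linear regression model, adjusted for its own D0 score. The sum of A and D is not used as the anxiety measure.

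Name HAD-A and HAD-D in criterion 4 of section 2.2.

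If the presence of depressive signs is meant as a threshold on D, the outcome is binary. The sponsor should then state its own definition before the data are seen and use a mixed generalized linear model for it, as 5.2 already does for the DN4.

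The cost is wording in two sections, one more model and one more secondary comparison. That comparison is an additional test at the general 5% alpha. No new data are needed: the schedule in 4.5 already collects the HAD at D0, M6 and M12.

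### The lean-mass and DN4 models do not list the D0 value that seven sibling secondary models adjust for, although it is collected for both (minor)

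*Combined protocol and SAP*

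**What the plan says.** Section 2.2 introduces the secondary objectives with "Compare between the 2 randomisation arms". Its criteria include "Percentage and weight of lean mass measured on an impedance scale at D0, M6 and M12" and DN4 positivity (score of 4 or more) at the same three visits. The schedule in section 4.5 puts DN4 and the impedance measurement at D0, M6 and M12.

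Section 5.2 gives one model sentence for each of nine secondary outcomes measured at these visits:

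- **D0 not listed (2).** Lean mass is "collected at D0 M6 and M12 and compared using a mixed linear regression model taking into account the repeated nature of the data". For DN4: "It will be compared between the two groups using a mixed generalized linear regression model taking into account the repeated nature of the data".
- **D0 listed (7).** VAS, isochrony, HAD, WPI, SSS, Tampa and EQ-5D-5L. For Tampa, for example: "The total score will be compared between the groups using a mixed linear regression model taking into account the baseline score on D0".

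The primary FIQR model is spelled out more fully. It is fitted "taking into account the baseline score at D0, the time effect", the time-by-group interaction and the repeated measurements, and then: "The comparison of the evolution of the score at M6 will be tested from the M6 contrast". None of the nine secondary sentences names time, the interaction or a visit contrast, and no sentence says that the primary model's terms carry over.

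**The concern.** Two outcomes are handled differently from seven siblings in the same section, and no reason is given. For these two the plan does not say whether D0 is a covariate, a response alongside M6 and M12, or unused. These choices give different precision for the same between-arm question, and the D0 value is available in every case.

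The missing time and interaction terms are an accompanying matter of clarity. M6 closes the programme, and M12 follows six months in which activity is the patient's choice (sections 4.2 and 4.5). A reader would want the two visits estimated separately, and the secondary sentences do not say that they will be.

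**Working it through.** **1. Term count (section 5.2).** Of nine D0/M6/M12 secondary models, D0 is listed in 7. Time is listed in 0, time-by-group in 0 and a visit contrast in 0. The monthly tracker model is not one of the nine, and FIQR at M12 is covered by the primary model.

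**2. The plan's own figure.** The 114 evaluable patients are reproduced by a two-sided 5% t-test with 80% power, a difference of 7 and SD 13.2: 56.8, rounded up to 57 per arm. The plan does not state the SD; 13.2 is the pilot study's 6-month value. The point does not depend on this figure; 114 serves below only as a reference size.

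**3. Lean mass.** The documents give no correlation, so r = 0.5, 0.7 and 0.9 are assumed, with equal variances (set to 1), the same correlation between all visits, complete data and separate M6 and M12 effects. The variance factor for the M6 contrast is:

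- D0 as covariate: 1 − r²
- D0 as response, separate arm means at D0: 2(1 − r)
- D0 as response, common D0 mean: 1 − r² in large samples, so essentially no loss
- D0 unused: 1

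The SE ratio to the covariate model is √(2/(1 + r)) for D0 as a response with separate means, and 1/√(1 − r²) for D0 unused. Power for an outcome with a hypothetical 80% under the covariate model is Φ(2.80/ratio − 1.96). Dividing 114 by the squared ratio gives the equivalent number of patients.

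| r | Response, separate means: ratio / equivalent n / power | D0 unused: ratio / equivalent n / power |
|---|---|---|
| 0.5 | 1.15 / 86 / 68% | 1.15 / 86 / 68% |
| 0.7 | 1.08 / 97 / 73% | 1.40 / 58 / 52% |
| 0.9 | 1.03 / 108 / 78% | 2.29 / 22 / 23% |

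The two columns meet at r = 0.5, where 2(1 − r) = 1. Above that, leaving D0 unused costs more.

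**4. DN4.** Simulation of a random-intercept logistic model fitted by maximum likelihood. Assumed inputs: 57 per arm; 50% prevalence at D0 and in controls; patient SD 1, 2 or 3; conditional log-odds effect at M6 of −1.2, −1.6 or −2.0 (odds ratios about 0.30, 0.20 and 0.14), half of it remaining at M12. The effects were chosen to put power near 70 to 80%. The M6 contrast was tested by a two-sided 5% Wald test in 1,500 runs per setting (Monte Carlo SE about 1.2 points).

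| Patient SD | D0 covariate | D0 response, with interaction | D0 unused |
|---|---|---|---|
| 1 | 71.2% | 50.9% | 70.1% |
| 2 | 75.8% | 61.1% | 68.3% |
| 3 | 79.7% | 70.4% | 65.5% |

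The covariate model gains 20.3, 14.7 and 9.3 points over D0 as a response, and 1.1, 7.5 and 14.2 points over D0 unused. Type I error was 3.2 to 5.9% in 750 null runs each. A separate 300-run simulation gave the same ordering at each SD, within about 6 points. Power is compared rather than SE because conditional log-odds scales differ between the models.

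**The case against.** The strongest reply is that the secondary sentences are shorthand. They do not name group either, although section 2.2 says that the arms are compared, so they cannot be complete term lists. The primary criterion defines how evolution is compared, and most secondary sentences reuse that word; the same model, abbreviated, is a natural reading. This stands, and it limits the point about time and interaction to a request for clarity.

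Second, D0 may be meant as a response. That is the natural reading of the lean-mass sentence, which lists D0 with M6 and M12. The DN4 sentence names no visit and does not speak of evolution, so it settles less. With a common D0 mean, the response form loses essentially nothing for lean mass. This also stands: not listing D0 is not an error in itself.

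A reader might infer three stronger things that the documents do not support:

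- *M6 and M12 will be pooled, with a loss of power.* The plan does not state this, so no such loss is claimed.
- *D0 will be ignored, as the worst case for both outcomes.* The lean-mass sentence itself includes D0. For DN4 at patient SD 1 and 2, D0 as a response does worse than D0 unused.
- *Every secondary objective asks for both visits.* Among the nine, only the pain objective does: "The evolution of pain intensity between the beginning of the treatment (D0), at 6 months (M6) and at 12 months (M12"). The general statement in section 1.1 about 6 and 12 months names no outcome, and for the others section 2.2 gives both visits only as measurement times.

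Finally, separate M6 and M12 contrasts for nine outcomes, with lean mass in two units, give (9 + 1) × 2 = 20 estimates, and the plan sets only a 5% alpha. They should therefore carry no multiplicity claim.

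**Conclusion.** The point holds as a minor one. Lean mass and DN4 are the only two of nine comparable secondary models that do not list the D0 value. Adjusting for it is a better-defined analysis and, in the cases worked through, at least as precise as the alternatives.

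The gain depends on what was intended. For lean mass it runs from essentially nil (common D0 mean) to an SE 1.15 to 1.03 times smaller than with D0 as a response with separate means, at assumed r of 0.5 to 0.9. It is larger only if D0 is unused and r exceeds 0.5. For DN4 it is about 9 to 20 points of power over D0 as a response, and about nil to 14 points over D0 unused, under assumed prevalence and deliberately large effects. No secondary outcome is powered in the plan, so these figures show direction and rough size and are not forecasts.

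The primary analysis, FIQR at M12 and the sample size are unaffected.

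**What to change.** In section 5.2, give lean mass (kg and %) and DN4 the plan's own primary-model form: M6 and M12 as responses and the D0 value as covariate. For DN4, the covariate is D0 status (score of 4 or more) in the generalized mixed model.

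Add one clarifying sentence for all nine outcomes: each model contains group, categorical time and their interaction, and the M6 and M12 between-arm contrasts are reported separately, as secondary estimates without a multiplicity claim. If D0 is to stay a response for either outcome, say so, state whether the arms share a D0 mean, and name the contrasts.

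The cost is wording only, since no new data or patients are needed. One small downside is that patients without a D0 value drop out of a covariate model, while section 5.2 analyses all randomised patients and its no-imputation statement concerns FIQR. A response model with a common D0 mean keeps them.
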